The primary observation to be made is the level of PaCO₂ in the arterial blood, specifically when the patient is insufflated and deflated during the surgery. As a result of the consistent pressure that the AirSeal® system maintains, CO₂ will be absorbed in lower levels when compared to the standard of care systems in which fluctuations in intra-peritoneum pressure are seen. Therefore, higher pressures will result in higher levels of CO₂ exchange in the blood, leading to increased vasodilation and lower pH levels.⁸ Given the potential benefit of using valve-less trocars during robotic prostatectomies as demonstrated in other laparoscopic abdominal procedures, the aims of this study are:

Aim #1) Describe the perioperative CO₂ absorption rates between the conventional and valve-less trocar groups via the end-tidal CO₂ and PaCO₂, at baseline, 60 minutes intraoperatively, and immediately following surgery. Optimal intraoperative levels for PaCO₂ and end tidal CO₂ should be between 33-37 mmHg. These values are expected to slowly rise throughout surgery due to CO₂ absorption. The anesthesiologist will make specific adjustments and alter ventilation settings throughout the surgery to prevent the values from elevating further once they reach 37-38 mmHg. Between 33-36 mmHg, no adjustments are made. Therefore, we will also examine the valve and valve-less trocar groups on their ability to maintain acceptable arterial blood gas (ABG) levels by comparing the number of interventions required by the anesthesiologist during the procedure between groups.

Aim #2) Compare the maximum intraoperative pneumoperitoneal pressure (mmHg), smoke evacuation quality (categorical), and overall operative times (minutes) between the conventional and valve-less trocar groups.

Aim #3) Compare pain scores through discharge from the preoperative and post-anesthesia care units (PACU) by monitoring self-reported pain ratings using an 11-point numerical rating scale (NRS-11) and pain medication usage via morphine equivalent dose (MED) units.

Table 1. Definitions of key variables.

Variable	Definition	Unit
CO ₂ absorption rate	Not directly measurable. We are using end tidal CO ₂ and PaCO ₂ to indirectly measure the absorption rate.	N/A
Arterial Blood Gases (ABGs)	Measurement of the pH level and the bicarbonate, oxygen, and carbon dioxide concentrations in arterial blood (HCO ₃ , PaCO ₂ & PaO ₂); important in diagnosis of	N/A

	many respiratory diseases.	

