For item (b)3, continuous values will be exported into individual patients-specific Excel spreadsheets with the assistance of the CareConnect Systems Analysts. This is due to the fact that there are far too many data points (ET CO₂, O₂ saturation, RR, BP, HR, TV, PIP, PEEP, every 1 minute for 120 minutes) to be manually extracted and subsequently manually entered into the Data Collection Tool by study staff. The biostatistician will perform individual analyses on these data sets, and calculate means and standard deviations to be entered into the Data Collection Tool.

For item (d)4, we are evaluating for oliguria in the immediate post-operative period (1900-0700 hours). Oliguria is infrequently viewed as a complication of laparoscopic surgery. The rate of urine output in

healthy patients undergoing laparoscopic surgery is measured during the period of CO₂ pneumoperitoneum and for several hours after desufflation. For patients that are discharged prior to the completion of the urine output collection (i.e., prior to 0700 hours postoperatively), they will be instructed to take home their urine collection canister and collection instructions to complete measurements following discharge. The Research Coordinator will then call the patient the following morning for the urine output measurement.

Table 3. Arterial Blood Gases (ABGs) monitoring schedule by anesthesiologist.

Timepoint	Definition
Baseline	At insertion of the catheter
60 minutes	60 minutes after insufflations
End of the procedure	Immediately at the end of surgery

We will be measuring the trend in arterial blood gases over time (Table 3). Optimal intraoperative levels for PaCO₂ and end tidal CO₂ should be between 33-37 mmHg. These values are expected to slowly rise throughout surgery due to CO₂ absorption. The anesthesiologist will make specific adjustments and alter ventilation settings throughout the surgery to prevent the values from elevating further once they reach 37-38 mmHg. Between 33-36 mmHg, no adjustments are made.

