Since the anesthesiologist will be adjusting ventilator settings at 37-38 mmHg to typically keep the end tidal CO₂ below 40 mmHg, we expect that there will not be a large amount of difference between standard and valve-less trocars regarding the ABGs. However, the ABGs will change over time, warranting the alteration of ventilator settings by the anesthesiologist. In other words, if the ABGs are same between the two groups but the anesthesiologist had to increase the respiratory rate or tidal volume to keep end tidal CO₂ low more so in the standard group than the valve-less, then we will conclude that the valve-less was better. Essentially, the ABGs are a sort of "control" whereby even if they are not different, it still allows us to know whether or not there was a real physiologic difference occurring, whether or not we saw a difference in the other measures that were adjusted in real time.

Table 4. Pain monitoring schedule by Pre-op and PACU RNs using NRS-11.

Timepoint	Definition
Baseline	Prior to surgery
Post-operatively	After surgery & after anesthesia completion
30 minutes post-operatively	30 minutes after surgical completion time (+/- 5 minutes)
60 minutes post-operatively	60 minutes after surgical completion time (+/- 5 minutes)
At discharge	Immediately prior to discharge from the PACU

Postoperative (post-anesthesia) pain will be evaluated at baseline, post operatively, once every thirty minutes for the first hour and every 8 hours until discharge (Table 4). Floor nurses (preoperative and PACU) will record pain scores reported by patients during structured interviews using an 11-point numerical rating scale (NRS-11), in which a rating of 0 corresponds to no pain, ratings of 1-3 indicate mild pain, 4-6 indicate moderate pain, and ratings of 7-10 correspond to severe pain (Appendix A).

Data will be collected using the forms in the Appendix. Data will be collected by a member of the research team (clinic nurse or clinical research coordinator). All data will be coded by subject number and de-identified. The designated clinical research coordinator will hold the key to subject codes in a locked cabinet and password-protected electronic file. Case reports formed with the coded key will be available only to the study staff.

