- General or specific changes in the subject's condition that render further treatment unreasonable or unsafe within the standards of clinical practice in the judgment of the Principal Investigator or treating physician

2.5 – Statistical Analysis

We will first compare the demographic and pre-operative clinical characteristics of the conventional and valve-less trocar groups to evaluate randomization fidelity. If any characteristics are found to be statistically significant between the groups, this will be accounted for in the analyses of the primary and secondary outcomes. We will describe all categorical variables as percentages and continuous variables with means and standard deviations.

Aim #1) Describe the perioperative CO₂ absorption rates between the conventional and valve-less trocar groups via the end-tidal CO₂ and PaCO₂ , at baseline, 60 minutes intraoperatively, and immediately following surgery. We will also examine the valve and valve-less trocar groups on their ability to maintain acceptable ABG levels by comparing the number of interventions required by the anesthesiologist during the procedure between groups.

We will describe the change in CO₂ and PaCO₂ levels at 3 intervals: baseline to 60 minutes, 60 minutes to end of surgery, and baseline to end of surgery to examine the trends in both groups. We will compare the conventional and valve-less trocar groups on the number of interventions required by the anesthesiologist to maintain acceptable pressure using Poisson regression. If a significant number of patients required no intervention we will use a zero-inflated model. Statistical significance will be set at p<.05. We will also compare CO₂ absorption rates between high pressure (>8mmHg) and low impact (≤8mmHg) procedures.

Aim #2) Compare the maximum pneumoperitoneal pressure (mmHg), smoke evacuation quality (categorical), and overall operative times (minutes) between the conventional and valve-less trocar groups.

We will compare the conventional and valve-less trocar groups on maximum pneumoperitoneal pressure and overall operative time using t-tests or Wilcoxon rank sum tests. We will compare the groups on evacuation quality using a chi-square test. Statistical significance will be set at p<.05.

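### PaCO₂ is called the primary observation but is only described; no primary test is named, and the rule for concluding superiority has no criterion for blood gases being the same

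*Combined protocol and SAP*

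**What the plan says.** **Role of PaCO₂ in Section 1.2.** "The primary observation to be made is the level of" PaCO₂ in arterial blood, during insufflation and deflation. The section predicts lower CO₂ absorption with the valve-less system, and Section 2.2 makes that the hypothesis.

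**Titration, Sections 1.2 and 2.3.** The anesthesiologist will "alter ventilation settings throughout the surgery to prevent the values from elevating further once they reach 37-38 mmHg". This applies to both PaCO₂ and end-tidal CO₂.

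**Role of PaCO₂ in Section 2.3.** Because of that titration, "we expect that there will not be a large amount of difference between standard and valve-less trocars regarding the ABGs". The gases are described there as a kind of control that is informative even without a difference. The same paragraph holds the only explicit conclusion rule in the plan: if the gases are the same but respiratory rate or tidal volume had to be raised more in the standard group, "then we will conclude that the valve-less was better".

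**Analysis, Section 2.5.** Imbalanced baseline characteristics will be accounted for in "the analyses of the primary and secondary outcomes", but no outcome is assigned to either class. Changes in CO₂ and PaCO₂ are described over three intervals. Six outcomes are then compared between arms, and under each of the three aims "Statistical significance will be set at p<.05".

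**The concern.** PaCO₂ has two roles that pull apart. In Section 1.2 it is the main measure on which a benefit should appear. In Section 2.3 it is a background check expected to show little difference, and the benefit should appear in the ventilation adjustments. Section 2.5 does not settle which role governs.

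Three things follow:

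- The stated primary observation has no planned between-arm inference.
- The conclusion rule depends on the blood gases being the same, and no analysis could show whether they are. A non-significant or unremarkable difference does not establish sameness.
- With no outcome designated as primary, readers of the final report cannot tell which of the six tests was meant to decide the question. The emphasis could be chosen after the results are known.

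**Working it through.** **1. Stated roles against planned analysis**

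| Variable | Role in 1.2 and 2.2 | Role in 2.3 | Analysis in 2.5 |
|---|---|---|---|
| PaCO₂ | Primary observation; proxy for the hypothesized lower absorption | Control, no large difference expected; must be the same for the rule to apply | Described over three intervals; no between-arm test or interval |
| Ventilation interventions | Also examined, under Aim 1 | Basis for concluding superiority | Poisson or zero-inflated model, p<.05 |

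The variable called primary is not tested. The variable that carries the conclusion is not called primary.

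**2. Between-arm tests named in Section 2.5**

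- Aim 1: number of interventions (one test).
- Aim 2: maximum pneumoperitoneal pressure, operative time, smoke evacuation quality (three tests).
- Aim 3: pain score, morphine equivalent dose (two tests).

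The total is six. The comparison of high-pressure with low-impact procedures is not between arms and has no named test, so it is not counted.

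**3. False-positive rate**

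The plan states no family-wise error rate, so there is no figure to reproduce. Sidedness is not stated; two-sided tests are assumed. With no true difference on any outcome and k independent tests, the chance of at least one p<.05 is 1 − 0.95^k.

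- All aims pooled, k = 6: 1 − 0.95⁶ = 0.265.
- Bound under any dependence: 6 × 0.05 = 0.30.
- By aim, if independent: Aim 1, 0.05; Aim 2, 1 − 0.95³ = 0.143; Aim 3, 1 − 0.95² = 0.098.

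The six outcomes share patients, so some correlation is likely. The documents give none. A simulation of six equally correlated two-sided z-tests (one million replicates) gives:

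| Assumed correlation | At least one p<.05 | At least one p<.05 favouring AirSeal |
|---|---|---|
| 0 | 26.5% | 14.1% |
| 0.3 | 24% | 12% |
| 0.5 | 21% | 10% |
| 0.8 | 14% | 7% |

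The nominal levels are 5% and 2.5%.

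**4. What 100 patients can say about sameness**

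Section 2.2 gives a total of 100. Assuming 50 per arm, an unadjusted 95% CI for a difference in means has half-width 1.96 × √(2/50) = 0.39 SD. Even an observed difference of exactly zero would leave differences of up to about 0.39 SD in either direction compatible with the data. Adjustment for baseline would narrow this by an amount the documents do not let us estimate. Whether that precision is enough depends on a margin, and the plan states none.

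**5. One primary test, or six co-equal tests**

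- One designated primary test: error rate 0.05 for the main claim.
- Six co-equal tests with Bonferroni: 0.05/6 = 0.0083 each.

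Assuming 50 per arm and 80% power, the detectable difference is (z for alpha + 0.842) × √(2/50):

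- At 0.05: (1.960 + 0.842) × 0.2 = 0.56 SD.
- At 0.0083: (2.638 + 0.842) × 0.2 = 0.70 SD.

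For an assumed effect of 0.5 SD, power falls from 71% to 45%. These figures are for a continuous outcome and only illustrate the price of splitting alpha.

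**The case against.** The best defence is that Aim 1 has two linked parts with loose labels. Section 1.2 says primary observation, not primary endpoint, and Aim 1 sets out to describe. It explains the titration and moves from there to counting interventions. Section 2.3 elaborates the pairing, and Section 2.5 follows it: describe PaCO₂, test interventions. On this reading, the test behind the conclusion already runs at 5%. That reading is coherent and lessens the conflict. It does not supply the missing assignment of primary and secondary outcomes, or a criterion for the gases being the same.

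Two stronger readings should be set aside.

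- A reader might infer that PaCO₂ is held equal by design and so cannot answer the hypothesis. The documents do not go that far. They expect no large difference, they put sameness as a condition, and adjustment starts only at 37-38 mmHg. PaCO₂ is constrained, not fixed.
- A reader might infer that the plan treats any significant test as success. No section says so, and the one stated rule concerns ventilator adjustments. What can be said is that nothing visible rules it out.

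The objection to the 26.5% also stands in part: it pools three separately stated aims and assumes independence and no true effect on any outcome.

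Finally, a figure at the end of Section 2.5 is not shown, so statements about absence apply to the visible text.

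**Conclusion.** The concern holds in a limited form. The plan gives PaCO₂ two roles that need reconciling, provides no between-arm inference for its own primary observation, and leaves the condition in its conclusion rule without an assessment. It also refers to primary and secondary outcomes without saying which are which, while naming six unadjusted tests.

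The exposure is at most 30% under any dependence. It is 26.5% if all aims are pooled and the tests are independent, and about 24% to 14% at assumed common correlations of 0.3 to 0.8. All of these assume two-sided tests and no true difference on any outcome. They describe what could happen if one result were chosen from the six. They are not the error rate of a rule the plan has adopted.

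This should be changed before analysis.

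**What to change.** 1. **Reconcile Sections 1.2 and 2.3** on whether PaCO₂ is the main measure or the supporting one.
2. **In Section 2.5, add a between-arm PaCO₂ comparison** at 60 minutes and at end of procedure, adjusted for baseline PaCO₂, with 95% CIs. Table 3 already schedules these samples. State in advance the margin within which the arms will be regarded as the same, and judge sameness by the interval against that margin. The margin is a clinical choice for the sponsor.
3. **Designate one primary test at .05** and label the others secondary and supportive. No alpha split is then needed. The choice is the sponsor's; the ventilation-intervention count is the candidate that fits the Section 2.3 rule, on two conditions:
   - Its definition must be consistent. Section 2.3 speaks of raising respiratory rate or tidal volume, Table 2 of adjusting ventilation settings, and Section 2.5 of interventions to maintain acceptable pressure.
   - The plan should acknowledge that the anesthesiologist who decides the interventions may not be blinded. Section 2.4 says single-blind without saying who is blinded.

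**Cost.** This takes wording in Sections 1.2, 2.3 and 2.5 and one added analysis of data already collected, with no change to clinical procedure. Secondary tests can no longer carry the main claim. The sample of 100 has no stated basis for any outcome, so the plan should say what it can detect on the chosen primary.

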HCO ₃	Amount of bicarbonate in the arterial blood. This is used to aid in diagnosis of metabolic acidosis or alkalosis.	mmol/L
PaO ₂	Partial pressure of oxygen in the arterial blood. This is the true measure of O ₂ build in the blood.	mmHg
PaCO ₂	Partial pressure of carbon dioxide in the arterial blood. This is the true measure of CO ₂ build up in the blood, and reflects whether the lungs are keeping up in expelling the extra CO ₂ from abdominal absorption.	mmHg
End tidal CO ₂	The level of carbon dioxide in the air exhaled from the body, as measured by the ventilator. Essentially, this reflects the amount of CO ₂ that the lungs are expelling due to CO ₂ absorption from the insufflations. This increases over the course of the procedure.	mmHg
"Blunted" end tidal CO ₂	A technical observation made regarding the shape of the end tidal CO ₂ curve on the capnogram displayed on the ventilator. This is an observation, not discretely measureable.	N/A
Tidal volume	The lung volume representing the normal volume of air displaced between normal inspiration and expiration when extra effort is not applied (i.e., normal/resting breathing).	ml
O ₂ saturation	Measure of how much oxygen the blood is carrying as a percentage of the maximum it could carry.	%
Pneumoperitoneal pressure	Measurement of air or gas in the abdominal (peritoneal) cavity.	mmHg
Peak inspiratory pressure (PIP)	Point of maximal airway pressure.	mmHg
Positive end-expiratory pressure (PEEP)	Pressure maintained in airways at end of exhalation.	mmHg
Smoke evacuation quality	Smoke evacuation occurs during surgical procedures where there is tissue ablation. Smoke evacuation systems capture the plume (smoke comprised of carbonized cell fragments, water vapor, and hydrocarbons) from vaporized tissue near its origin before it becomes air-dispersed and deposits in the respiratory tracts of the surgical team.	Categorical (see Appendix B)

2.0 - METHODS

2.1 - Study Population

Adult male patients \geq 18 years of age with prostate cancer who are eligible and electing to undergo robotic prostatectomy surgery at OhioHealth Dublin Methodist Hospital between March 1, 2016 and February 28 2017 (12 months). Exclusion criteria to robotic surgery include:

- 1) Cirrhosis or liver failure (Child-Pugh class A, B, or C) or clinical suspicion of liver failure
- 2) Ascites
- 3) Uncontrolled diabetes [as reported by the pre-anesthesia testing (PAT) physician]

4) Renal insufficiency (serum creatinine level > 3.0 mg/dl)

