The following data points are all routinely collected for patients who choose to undergo robotic prostatectomy, via the OhioHealth electronic medical record, CareConnect. We will collect similar data points for patients electing enrollment in this trial which include the following listed below (Tables 2-4). Data points which are not collected in the standard of care setting are noted below in **bold face type**. Only the study staff will have access to the database created solely for use in this study. Data will be de-identified following study completion, prior to statistical analysis.

Table 2. Study Variables by Operative Time-point

(a) Preoperative data [collected at the preoperative office/clinic visit, in the office setting, or in

the pre-anesthesia testing (PAT) office visit]:

- 1) Medical record number
- 2) Patient name
- 3) Patient date of birth
- 4) Phone number
- 5) Email address
- 6) Body mass index (BMI)
- 7) Weight (lb)
- 8) Medical history
- 9) Surgical history (major only)
- 10) Serum creatinine (most recent prior to surgery) (mg/dl)
- 11) Hemoglobin (g/dl)
- 12) Preoperative pain measured by the NRS-11 (Appendix A)**

(b) Intraoperative data:

- 1) Details of the surgical procedure
- 2) The number, size(s), and locations of ports used (standard protocol vs. deviation from standard protocol)
- 3) Values obtained from anesthesia report at baseline, 60 minutes after insufflations, and at the end of procedure and mean and standard deviation calculated from continuously recorded values:
 - a) End tidal CO₂ (mmHg)
 - b) O₂ saturation (%)
 - c) Respiratory rate
 - d) Blood pressure
 - e) Heart rate
 - f) Tidal volume (ml)
 - g) PIP (peak inspiratory pressure) (mmHg)
 - h) PEEP (positive end-expiratory pressure) (mmHg)
- 4) CO₂ absorption rate via arterial blood gases (ABGs) at baseline, 60 minutes after insufflations, and at the end of the procedure [PaCO₂ (mmHg), HCO₃ (mmol/L) & PaO₂ (mmHg)]
- 5) Number of times the anesthesiologist intervenes to adjust ventilation settings throughout the surgery to prevent the values from elevating further once they reach 37-38 mmHg
- 6) Estimated blood loss (EBL, in ml)
- 7) Core body temperature (after trocar placement, at 30 minutes, at 60 minutes, and at end of procedure; Fahrenheit)
- 8) Insufflation time (minutes)

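### Aim #1 gauges CO2 absorption by partial pressures that the anesthesiologist holds down, and the minute-by-minute ventilation data that could correct for this are never combined with them

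*Combined protocol and SAP*

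**What the plan says.** - **Hypothesis (section 2.2).** CO2 absorption will be lower with the valve-less system than with the conventional one.
- **Measure (section 1.2, Table 1).** The absorption rate is "Not directly measurable. We are using end tidal CO", with PaCO2 as the other indirect measure. Of end-tidal CO2 the table says "Essentially, this reflects the amount of CO" being expelled. Of PaCO2 it says that it "reflects whether the lungs are keeping up in expelling the extra CO" taken up from the abdomen. Both carry the unit mmHg. The text of section 1.2 makes PaCO2 the primary observation.
- **Titration (sections 1.2 and 2.3).** Ventilator settings are changed "to prevent the values from elevating further once they reach 37-38 mmHg".
- **Expected result (section 2.3, after Table 3).** Because of that titration, "we expect that there will not be a large amount of difference between standard and valve-less trocars regarding the ABGs". The same paragraph says that equal blood gases, with larger rises in respiratory rate or tidal volume in the standard group, would favor the valve-less trocar.
- **Data (section 2.3).** Table 2(b)3 lists "Values obtained from anesthesia report at baseline, 60 minutes after insufflations, and at the end of procedure", including end-tidal CO2, respiratory rate and tidal volume. These are also exported "every 1 minute for 120 minutes", then reduced to means and standard deviations.
- **Analysis (section 2.5, Aim #1).** CO2 and PaCO2 changes are described for "levels at 3 intervals: baseline to 60 minutes, 60 minutes to end of surgery, and baseline to end of surgery". The only Aim #1 comparison with a named method is the intervention count, by Poisson or zero-inflated regression. High-pressure and low-impact procedures are also compared on CO2 absorption.

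**The concern.** A partial pressure reflects CO2 load relative to ventilation. The amount of CO2 cleared per minute needs both. Table 1's own account of PaCO2, as a sign of whether the lungs keep pace, describes such a balance. When ventilation is raised in response to the measured value, the arm that absorbs more CO2 is ventilated more, and the difference in partial pressure shrinks or changes sign.

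Section 2.3 sees this and turns to changes in respiratory rate and tidal volume. Section 2.5 analyzes neither. It keeps only the number of interventions, so one small adjustment and one large one count the same. No section combines the logged respiratory rate, tidal volume and end-tidal CO2.

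At stake is whether the trial can estimate the quantity in its hypothesis. The high-pressure v low-impact comparison inherits the same measure.

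**Working it through.** **Inputs from the documents.** Adjustment at 37-38 mmHg; 100 patients in total; significance at 0.05. The documents give no effect size, standard deviation, power or allocation ratio, so there is no planned figure to reproduce. Everything else below is assumed: 50 per arm, two-sided tests, metabolic CO2 output, absorbed CO2, ventilator step sizes, spreads and dead space.

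**1. Fixed example.** At steady state, PCO2 = 0.863 x CO2 output / alveolar ventilation (mmHg, ml/min, L/min). With metabolic output 200 ml/min and baseline 33 mmHg, ventilation is 0.863 x 200 / 33 = 5.23 L/min. Ventilation is raised in fixed steps until PCO2 falls below 37 mmHg.

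| Absorbed CO2, conventional v valve-less (ml/min) | Step | PCO2 (mmHg) | Difference |
|---|---|---|---|
| 40 v 20 | none | 39.6 v 36.3 | +3.3 |
| 40 v 20 | 10% | 36.0 v 36.3 | -0.3 |
| 40 v 20 | 20% | 33.0 v 36.3 | -3.3 |
| 60 v 30 | 10% | 35.5 v 34.5 | +1.0 |
| 60 v 30 | 20% | 35.8 v 31.6 | +4.2 |

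The PCO2 difference can vanish, reverse or keep its sign, depending on step size. Ventilation x PCO2 recovers 240 v 220 ml/min in every 40 v 20 row.

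**2. Steady-state simulation.** 20,000 per arm; baseline PCO2 34 (SD 1) mmHg, metabolic output 200 (SD 25), absorption SD 15 ml/min, trigger 37.5 mmHg; absorption 40 v 20 ml/min.

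| Step | Mean PCO2 difference (mmHg) | Power, 50 per arm | Interventions per patient |
|---|---|---|---|
| 5% | +0.57 | 0.86 | 2.28 v 0.84 |
| 10% | +0.28 | 0.25 | 1.40 v 0.59 |
| 20% | -0.03 | 0.03 | 0.96 v 0.49 |

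With 60 v 30 ml/min the differences are +0.24, +0.09 and +0.14 mmHg, so at 5% and 10% steps a larger true effect shows a smaller PCO2 difference. With 30 v 15 and 20% steps the difference is -0.21, the wrong sign.

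**3. The planned count in the same simulation.** Poisson approximation: z = ln(rate ratio) / sqrt(1/events + 1/events).
- 10% steps: ln(1.40/0.59) = 0.864; SE = sqrt(1/70 + 1/29.5) = 0.220; z = 3.94; power about 98%.
- 20% steps: ln(0.96/0.49) = 0.673; SE = sqrt(1/48 + 1/24.5) = 0.248; z = 2.71; power about 77%.

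The count can also fail. Take baseline 34.5 mmHg, trigger 37.5 and 25% steps. A 10% rise in load gives 34.5 x 1.10 = 38.0, and a 20% rise gives 34.5 x 1.20 = 41.4. Each arm needs exactly one step, ending at 38.0/1.25 = 30.4 and 41.4/1.25 = 33.1. The count is 1 v 1, although one arm absorbs twice as much.

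**4. Trial-level simulation.** 1,500 trials in each of 24 scenarios, 50 per arm. Baseline output 200 (SD 25) ml/min; baseline end-tidal 34.5 (SD 1) mmHg; reading noise SD 0.7 mmHg; index noise 5%; metabolic drift SD 5% or 10%; dead space 150 of 520 ml; trigger 37.5 mmHg; steps of 10, 15 or 25% by rate or by tidal volume, at least 10 minutes apart.

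| Absorption (ml/min) | End-tidal change at 60 min: power; wrong sign | Index ratio: power; wrong sign |
|---|---|---|
| 20 v 40 | 9-34%; 6-28% | 88-100%; under 0.5% |
| 30 v 40 | 4-20%; 13-41% | 34-59%; 1-6% |

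A further run, again with assumed inputs, gave 3-25% against 96-100% for 20 v 40. There the Poisson count had 91-100% power at 5-10% steps and 1-24% at 25% steps. For 30 v 40 the count was mostly weak.

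**5. Limits of the index.** With tidal volume 500 ml and dead space 150 ml, raising effective ventilation 20% through tidal volume takes it to 150 + 350 x 1.20 = 570 ml. The index then rises 570/500 = 1.14 against a true 1.20. Dead space of 120 to 180 ml gives 1.15 to 1.13. Subtracting the correct dead space restores 420/350 = 1.20. If rate is raised instead, the index gives 1.20. Metabolic CO2 stays in the index, so a doubling of absorption from 20 to 40 ml/min appears as 240/220 = 1.09.

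**The case against.** The strongest reply is that the plan already answers this. Section 2.3 predicts the masking, says how equal blood gases should be read, and section 2.5 formally compares interventions between arms. That stands in large part: with small steps and a twofold difference in absorption, the count separates the arms well. What remains is that it ignores step size and that section 2.5 names no analysis of respiratory rate or tidal volume.

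Section 2.5 also specifies no t-test on end-tidal change. The power figures for end-tidal CO2 therefore show how little the described values would reveal; they are not the power of a planned test.

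A reader might call Table 1's statement that absorption cannot be measured directly an error. It is not: the proposed index is indirect too, since it includes metabolic CO2 and dead space. Table 1 also gives end-tidal CO2 in mmHg and says only that it reflects the amount expelled.

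A reader might also infer that the partial pressures will usually point the wrong way. Neither the documents nor the calculations support that. The documents give no step size, and average reversal in the steady-state simulation was small. An example that leaves the lower-load arm untouched at 38.0 mmHg would break its own 37.5 trigger; treating both arms alike gives 30.4 v 33.1, the correct direction.

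Feasibility is a fair question. The protocol does not say when the 120 minutes start or how long procedures last.

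**Conclusion.** The concern holds in a limited form. End-tidal CO2 and PaCO2, under titration at 37-38 mmHg, are weak measures of the absorption hypothesis, and the planned count repairs this only in part. Under the assumed inputs at 20 v 40 ml/min, end-tidal change had 9-34% power and the index 88-100%. The count ranged from 91-100% at small steps to 1-24% at 25% steps. At 30 v 40 ml/min even the index reached only 34-59%.

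These figures are illustrative. They rest on assumed absorption, step sizes, variability and equal allocation. With 5% steps the steady-state simulation left PCO2 with 86% power, so masking is likely rather than certain. The documents do not support saying that Aim #1 as a whole would miss a real effect, because the count is part of it. The point is a worthwhile, low-cost improvement to the outcome measure and does not invalidate the design.

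**What to change.** **Section 2.5, Aim #1.**
- Prespecify a CO2 elimination index: respiratory rate x tidal volume x end-tidal CO2, computed minute by minute before the export is reduced to means, because a product of means is not the mean of the products.
- Per patient, take the log ratio of the mean index around 60 minutes after insufflation to the mean over ventilated minutes before insufflation. Do the same at the end of the procedure. State the windows in advance (for example, about 10 minutes around 60 minutes).
- Compare the randomized arms by linear regression with a 95% confidence interval.
- Repeat after subtracting a range of assumed dead space from tidal volume.
- Make this the main between-arm measure for the section 2.2 absorption hypothesis, and use it in the high-pressure v low-impact comparison. Keep the intervention count, PaCO2 and end-tidal CO2 alongside.

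**Table 1.** Keep absorption as indirectly measured, name the index as the indirect measure, and state that end-tidal CO2 and PaCO2 depend on ventilation.

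**Check first.** Confirm that the 120-minute export covers the baseline and end windows. If it does not, use the baseline and end-of-procedure values in Table 2(b)3, after confirming that baseline there means ventilated and before insufflation.

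**Cost.** SAP wording and a few lines of code. No new patients are needed, and no new measurements provided the coverage check succeeds. The index remains a proxy: it includes metabolic CO2 and dead space, and it understates the rise when tidal volume is the setting raised. That error is conservative only if dead space does not differ by device. No change to ventilator practice is proposed.
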